After a run-in period of 2 hours whereby the participants are using the AP algorithms, participants will eat self selected meals around 10 am. During the R-AP study only, another meal will be given four hours later around 2 pm. The self selected meals will have a minimum of 45 g of carbohydrates, and a maximum of 120 g of carbohydrates. These self selected breakfasts will be identical across both study sessions. Participants will not enter a meal bolus for the meals. CBG and blood ketone measurements will be taken every 30 min (for safety purposes only, not for input into the AP systems) until study discharge. If CBG >250mg/dL before the lunch meal, then study will be stopped early and the participant will be given the option to return on a different day for the second meal.

The study will be stopped if:

- (1) the CBG reaches > 300 mg/dL with ketones > 0.5 mM,
- (2) the CBG reaches > 300 mg/dL for over an hour (even when ketones are <0.5 mM),
- (3) the CBG reaches > 450 mg/dL,
- (4) participants exhibit nausea or vomiting or both.

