The closed-loop study will be stopped and open-loop control will be resumed under the guidance of the on call study investigator if any of the following occur after the start of the study: 1)

capillary blood glucose falls to < 40 mg/dl at any time point, 2) serum ketones are above 1.5 mM at any time and 3) seizure or unconsciousness associated with hypoglycemia.

Entire study stopping rules

Triggers for reporting unanticipated problems are seizure, hospitalization, death or any other occurrence considered serious by the PI. If any studies are stopped for severe hypoglycemia or diabetic ketoacidosis, then the entire study will be halted. Severe hypoglycemia is defined as event that required the assistance of another person due to altered consciousness, and required another person to actively administer carbohydrate, glucagon, or other resuscitative actions. Diabetic ketoacidosis is classified as: symptoms such as polyuria, polydipsia, nausea, or vomiting, serum ketones >1.5 mmol/L or moderate/large urine ketones, either arterial blood pH<7.3 or venous pH<7.24 or serum bicarbonate <15, and treatment provided in a health care facility. If an event of severe hypoglycemia or diabetic ketoacidosis should occur, the study will be halted and a description of the serious adverse event and a new risk mitigation plan will be submitted to the FDA. The study will only resume once FDA approval is received. In addition, if there is any unexpected event such as death or patient hospitalization, the studies will be stopped until the root cause is evaluated.

Description of the MPC and R-AP algorithms

Our MPC algorithm uses a glucoregulatory model to predict glucose outcomes over a predicted horizon (Np), and mathematically solve for the optimal insulin doses across the control horizon (Nc) to bring the participant to target. The model is updated at each timestep by a Kalman filter, which uses the difference between CGM observations and model predictions to update the physiologic model states. In short, a model-predictive controller uses a physiologic model to calculate how much insulin is required to bring someone to glucose target, and these predictions are adapted to the specific participant using a Kalman filter.

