Missing data: Missing sensed glucose values will be interpolated for up to 30 min segments. Longer periods of missing data will be omitted if they represent <3% of observation time (which will be truncated if a participant leaves the study early). If the missing data are >3% of observation time, we will use available CBG values to interpolate or impute using measurements. In the case that >2 participants fail to complete the study, we will analyze the primary outcome under multiple imputation using baseline values.

Confidentiality and Protection of Human Subjects RISKS and BENEFITS

Risks: The risks of the protocol procedures are considered minor. Nonetheless, since pumps and sensors used within automated glucose control systems are imperfect, there is a risk for hyperglycemia and hypoglycemia All studies will have frequent glucose and ketone samplings and a member of the study staff will be present for studies with a study investigator on call at all times.

Rarely, there can be allergic responses to insulin, such as skin redness, hives, itching of the skin, swelling of the mouth, or breathing difficulties. These reactions are considered very unlikely.

There is a small risk of sensor fracture, and in such a case, a piece of the sensor could be left in the tissue after sensor removal. For this reason, the study investigator will inspect each removed sensor for the possibility of breakage or fracture. Any evidence of sensor breakage will be recorded and reported to FDA and the sensor company.

Benefits: The participant may not directly benefit from being in this study; however, their participation may help to advance automated insulin delivery technology.

COSTS:

Participants will receive \$340 for completion of all study visits. If a participant withdraws early from the study, compensation will be given as follows: \$40 for the run-in visit and \$150 for each of the 2 study visits. There is no compensation for the screening visit. If a participant is asked to repeat a study due to technical problems, he/she will receive an additional \$150.

Monitoring Entity:

This investigation will be monitored by the co- investigator [name] MD. [name] has no commercial interest in any of the companies which manufacture any of the devices used in this

IRB 23343 Protocol v5 NCT05083559

study. Drs. [name], [name] and [name] are inventors on patents regarding the algorithms.

Data Collection:

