Any adverse event (AE) and/or unanticipated problem (UP) will be reported to the investigator monitor immediately by one of the investigators. Hypo- and hyperglycemia will not be considered AEs unless participant has positive ketones or displays symptoms of hypoglycemia such as: loss of consciousness, slurred speech, hospitalization or EMS services called. One of the investigators will always be on-call during the closed-loop studies and will write up a description of the adverse event/unanticipated problem. All reportable new information (RNI) will be reported to the IRB within five calendar days after the PI learns of the event. RNI is any information that might meet the regulatory definition of an unanticipated problem involving risks to participants or others or serious or continuing noncompliance that might impact the criteria for IRB approval. The report will be submitted to the IRB by the principal investigator or study coordinator. A summary of all UP's and adverse events, including those that do not meet the requirement for RNI, will be submitted with the continuing review. The FDA will be notified of any unanticipated adverse event related to the use of the study device. Notification will be made within 10 days after the Principal Investigator becomes aware of the event.

Confidentiality Procedures:

To protect confidentiality, standard institutional practices will be followed as described in the OHSU Information Security and Research Data Resource Guide

(http://ozone.ohsu.edu/cc/sec/isg/res_sec.pdf) to maintain the confidentiality and security of data collected in this study. Study staff will be trained regarding these procedures. See IRB protocol 19858 for a complete description of the confidentiality and security of the study data collected during this study to be stored in the OregonAPC repository.

[figure not shown]
Data for this project will be stored in an AWS server developed by our group that has undergone a security review.

Paper files will be stored in locked filing cabinets in restricted access offices at OHSU. After the study, source documents will be maintained at the participating clinical center (or offsite record storage facilities) 2 years after a marketing application is approved for our group's decision support device or discontinuance of pursuit of marketing approval.

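### Visits stopped for ketone-free hyperglycemia or symptom-free CBG below 40 mg/dL are normally not adverse events, no endpoint counts them, and truncation can flatter both primary endpoints

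*Combined protocol and SAP*

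**What the plan says.** - **AE definition (Monitoring Procedures).** "Hypo- and hyperglycemia will not be considered AEs unless participant has positive ketones or displays symptoms of hypoglycemia"; hospitalization and an emergency call appear among the listed examples. No cut-off is given for positive ketones.
- **Hyperglycemia stops (1 day Treatment Visits).** Rule (2) stops the visit if "the CBG reaches > 300 mg/dL for over an hour (even when ketones are <0.5 mM". Rule (3) applies above 450 mg/dL and carries no ketone condition.
- **Hypoglycemia stop (Individual study stopping rules).** Closed loop ends if "capillary blood glucose falls to < 40 mg/dl at any time point". No symptom is required.
- **Missing data (Statistical methods).** Gaps are judged against 3% of observation time, "which will be truncated if a participant leaves the study early". For larger losses: "In the case that >2 participants fail to complete the study, we will analyze the primary outcome under multiple imputation using baseline values".
- **Endpoints.** Incremental AUC (iAUC) is a sum of CGM values above the starting value over 4 hours after the first meal; the other primary endpoint is percent of time at 70-180 mg/dL over the same window. Secondary endpoints include percent of time below 54, below 70, above 180 and above 250 mg/dL, carbohydrate treatments, and provider-given insulin injections for hyperglycemia. None is a count of stopped visits.
- **After a stop.** When rules (1)-(3) are met, the investigator calculates a bolus with correction, given by Omnipod, syringe or the participant's own pump. Discharge from clinic allows an optional repeat of a visit that ended early and does not say which visit is analysed.

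**The concern.** A rule-triggered stop is the clearest sign that a system failed to control the meal. Under this plan that event has no line of its own, because it is normally not an AE and is not an endpoint. If observation is cut at the stop, a cumulative endpoint such as iAUC shrinks because the visit went badly enough to be ended. Time in range rises, because the early in-range minutes are divided by a shorter total.

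The distortion favours whichever system is stopped more often. The documents give no expected stop rates, so its direction is unknown. The Power Analysis section says the study is meant to inform a larger trial on feasibility and variability, and the stop rate by system is central to that purpose.

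**Working it through.** The plan states no figure to reproduce: the 15 participants rest on feasibility, and no SD or effect size is given. The check traces the rules and then uses assumed glucose curves.

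**1. Which stops fall outside AE reporting**
- Rule (1) and the separate ketone stop above 1.5 mM involve ketones, and seizure or unconsciousness is a symptom. These would ordinarily be AEs, subject to the undefined ketone cut-off.
- Rules (2) and (3) without positive ketones, and CBG below 40 mg/dL without symptoms, normally are not.

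**2. Smooth assumed curve** (5-minute CGM values, start 150, peak 350 at 110 min, end 260 at 240 min)

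Rise: G(t) = 150 + 100[1 − cos(πt/110)]. Fall: G(t) = 350 − 45[1 − cos(π(t − 110)/130)]. iAUC is the trapezoidal sum of G − 150. The first value above 300 is at 75 min, so one hour has passed at 135 min. On a 30-minute CBG schedule, the readings at 90, 120 and 150 min span exactly one hour.

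| Window | iAUC (mg/dL·min) | Share of full | In 70-180 | Above 250 |
|---|---|---|---|---|
| 0-135 min | 15,932 | 51% | 6/28 = 21.4% | 16/28 = 57% |
| 0-150 min | 18,731 | 60% | 6/31 = 19.4% | 19/31 = 61% |
| 0-240 min | 31,150 | 100% | 6/49 = 12.2% | 37/49 = 76% |

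**3. Stopped against milder completed visits** (assumed start 140, linear rise 2 mg/dL/min, then a plateau)

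With plateau P, the rise lasts τ = (P − 140)/2 min, and iAUC to time T is ½τ(P − 140) + (P − 140)(T − τ).
- P = 320: 300 is reached at 80 min and the rule (2) stop comes at 140 min. iAUC = ½·90·180 + 180·50 = 17,100. Over the full window it is 8,100 + 180·150 = 35,100.
- P = 240, completed: ½·50·100 + 100·190 = 21,500.
- P = 280, completed: ½·70·140 + 140·170 = 28,700.
- Time in range: 180 is reached at 20 min on every curve, so the stopped visit scores 20/140 = 14.3% and the completed visits 20/240 = 8.3%.
- Time above 250, reached at 55 min: 85/140 = 60.7% for the stopped visit, 0% for the completed P = 240 and 185/240 = 77.1% for the completed P = 280.

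The stopped visit therefore beats both milder completed visits on both primary endpoints. Across five assumed combinations (starts 110-160, rises 1.5-3 mg/dL/min, plateau 320), truncation lowers iAUC by about 41 to 60%.

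**4. Do the missing-data rules catch it?**
- In step 3, (240 − 140)/240 = 41.7% of the window is lost. Because observation time itself is shortened, this counts as 0% missing under the 3% rule.
- Imputation needs at least 3 non-completers. With an assumed stop risk p per participant, the chance of 1 or 2 stops among 15 is 15p(1 − p)^14 + 105p²(1 − p)^13: 50% at p = 0.05, 61% at 0.10 and 36% at 0.20. When imputation does start, it covers only the primary outcome and uses baseline values.

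**The case against.** A reader might infer that these failures vanish from both the efficacy and the safety results. The documents do not support that:
- Truncation keeps every reading before the stop, in every glucose endpoint. The smooth curve cut at 135 min still shows 57% of time above 250 mg/dL and a mean of 267 mg/dL.
- Injections for hyperglycemia are a secondary endpoint aimed at this kind of event. The cover is partial, since insulin given through the Omnipod or own pump may not count as an injection.
- A CBG below 40 mg/dL would ordinarily show in percent below 70, percent below 54 and carbohydrate treatments. Cutting the visit at the low drops the recovery, which would tend to raise those percentages. For hypoglycemia stops the gap is therefore the missing count, not flattered time low.

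Truncation at a rule-triggered stop is also inferred. The missing-data text speaks of leaving the study early, while CGM monitoring continues after a stop under rules (1)-(3), so data may exist for the whole window. This ambiguity stands. But post-stop CGM would reflect investigator-dosed insulin and would also mask the system's own performance, so a stop count is useful either way.

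The size depends on the curve and on CBG timing. In the smooth example the value at 180 min is 299.6 mg/dL, so scheduled 30-minute checks might never show more than an hour above 300. The percentages illustrate the mechanism and do not forecast its size.

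Leaving uncomplicated excursions out of AEs, when meal boluses are withheld on purpose, is a defensible design choice, and nothing here asks to change it.

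**Conclusion.** The point holds as a reporting gap with a conditional bias. Ketone-free stops under rules (2) and (3), and symptom-free stops below 40 mg/dL, are normally outside AE reporting, and no endpoint counts them; this follows from the text alone.

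If truncation applies to a stopped visit, hyperglycemia failures are attenuated in both primary endpoints and show only indirectly in secondary ones. On the smooth assumed curve, 51 to 60% of the full-window iAUC remains and time in range reads 19 to 21% instead of 12%. The curves and stop risks are assumptions; the documents supply neither.

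A reader might also infer that a repeat visit erases the failed one. The plan does not say so; it only leaves open which visit is analysed.

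**What to change.** Leave the clinical stopping rules and the AE definition unchanged.

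1. Add a secondary safety endpoint: number and percent of visits stopped, by system and by each criterion under 1 day Treatment Visits and Individual study stopping rules, with time to stop.
2. List every such stop in the safety tables, whether or not it is an AE.
3. State in Statistical methods that the original stopped visit, not an optional repeat, is the one analysed.
4. Add a sensitivity analysis of both primary endpoints that treats a rule-stopped visit as a failure, for example by worst rank, rather than scoring only the truncated window.

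Items 1 and 2 expose a difference between systems but do not correct the primary endpoints, which is why items 3 and 4 are needed. CBG and ketones are already measured every 30 minutes, so no new measurement is required. The listed case report forms include no separate termination form, so the visit forms should carry the stop reason and time if they do not already. The cost is one endpoint line, one table, a few sentences of analysis text, and a safety summary that may look slightly less favourable.

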Appendix A: Devices
Insulet Omnipod insulin management system

iPancreas with Dexcom G6 Continuous Glucose Monitoring System which includes Sensor and Sensor Transmitter

Contour Next Blood Glucose Meter

Abbott Precision Xtra Meter

Appendix B: Hypoglycemia Awareness questionnaire: This survey item will be used to categorize awareness or having reduced awareness of hypoglycemia.

1. Check the category that best describes you: (check one only)
 □ I always have symptoms when my blood sugar is low (A) □ I sometimes have symptoms when my blood sugar is low (R) □ I no longer have symptoms when my blood sugar is low (R)
2. Have you lost some of the symptoms that used to occur when your blood sugar was low? ☐ Yes (R) ☐ No (A)
 3. In the past 6 months how often have you had moderate hypoglycemia episodes? (Episodes where you might feel confused, disoriented, or lethargic and were unable to treat yourself). □ Never (A) □ Once or twice (R) □ Every other month (R) □ Once a month (R) □ More than once a month (R)
4. In the past year, how often have you had severe hypoglycemia episodes? (Episodes where you were unconscious or had a seizure and needed glucagon or intravenous glucose?)
 Never (A) 1 time (R) 2 times (R) 3 times (R) 4 times (R) 5 times (R) 6 times (R) 7 times (R) 8 times (R) 9 times (R) 10 times (R) 11 times (R) 12 or more times (R)

	iten in the last month have you had readings < 70 mg/dl with symptoms?
□ 1 t	o 3 times
□ 1 t	ime/week
\Box 2 t	o 3 times/week
□ 4 t	o 5 times/week
□ Al	most daily
6. How of 6<5;	ten in the last month have you had readings < 70 mgdl, without symptoms? R: 5<6, A:
□ Ne	ever
□ 1 t	o 3 times
□ 1 t	ime/week
\Box 2 t	o 3 times/week
□ 4 t	o 5 times/week
	most daily
7. How lo	w does your blood sugar need to go before you feel symptoms?
□ 60	-69 mg/dl (A)
□ 50	-59 mg/dl (A)
□ 40	-49 mg/dl (R)
\Box < 4	40 mg/dl (R)
8. To wha	t extent can you tell by your symptoms that your blood sugar is low?
□ Ne	ever (R)
	arely (R)
	metimes (R)
	ten (A)
	ways (A)

Date: January 31, 2022

Appendix C: Alert Manager Specifications

#	NAME: Activation criteria	Clearing Criteria	Algorithm specifics	Notificati on to participa nt	Re- fire Time (min)	Refrac tory Period (min)	Coordin ator push	Investi gator push	Waiti ng perio d
4	cbg_equal_or_under_4 0: CBG ≤ 40 mg/dl AND alert 4 not active	User enters CBG > 40 mg/dL after 15 minutes. Once rescue carb are entered, the waiting period starts. If CBG ≥70 at any time, alert clears.	None	"Blood glucose is below 40 mg/dl. Please take 30 gm of rescue carbohyd rates and recheck your blood glucose level in 15 minutes."	5	-	Immediately	Immediately	Waiti ng perio d ends whe n alert 13 is servi ced OR clear crite ria is met
5	cbg_under_70: CBG < 70 mg/dl AND alert 5 not active AND alert 4 not active	CBG entry ≥70 clears alert. Once rescue carbs are entered, the waiting period starts. Alert clears if activation of alert 4 is met	None	"Blood glucose is below 70 mg/dl. Please take 15 gm of rescue carbohyd	15	-	After 1st re- fire	After 2nd re- fire	Waiti ng perio d ends whe n alert 13 is servi

				rates and recheck your blood glucose level in 15 minutes.					ced OR clear crite ria is met
6	sensor_glucose_low: Sensor glucose < LOW_THRESH AND alert 4 AND alert 5 AND alert 6 not active or refractory & no CBG within last 15 minutes	CBG check OR sensor ≥ LOW_THRESH OR extreme_low_sen sor_glucose is active.	For MPC, LOW_THRESH = 70 mg/dL	"Sensor glucose is below LOW_TH RESH mg/dl. Please perform a blood glucose check now."	15	60	After 1st re- fire	After 2nd re- fire	-
7	cbg_equal_or_over_30 0: CBG ≥ 300 mg/dl AND alert 27 not active or refractory AND alert 7 not active or refractory	Ketone check	None	"Blood glucose is above 300 mg/dl. Please check the insulin pod for leaking or detachm ent and check ketone	30	120	After 1st re- fire	After 2nd re- fire	-

				levels now."					
8	sensor_glucose_high: Sensor glucose ≥ 300 mg/dl for 30 minutes within the last 45 minute period AND alert 8 AND alert 7 AND alert 27 not active or refractory AND no CBG in last 30 minutes	CBG check. OR sensor < 300	None	"Sensor glucose is over 300 mg/dl. Please perform a blood glucose check now."	30	60	After 1st re- fire	After 2nd re- fire	-
1 0	Insulin_meal_bolus_fail ure: If 50% of meal bolus is still not delivered after 20 minutes.	Auto clears	None	Insulin bolus failed to deliver, please contact the study investiga tor.	-	-	Immedi ately	Immedi ately	-
1 3	recheck_cbg: Alert 4 OR alert 5 in waiting period for 15 minutes	CBG recheck		"Please perform a blood glucose check now."	20	-	After 1st re- fire	After 2nd re- fire	-
1 4	no_data_connection: No connection to the internet or data for 40 minutes	Phone connects to a wifi network or regain cell service		There is no connecti on of the phone to the internet. Please move	40	-	-	-	-

			back into cell phone or wifi range.					
1 7	transmitter_not_reporti ng: Sensor is out of date for > 20 minutes AND alert 17 AND alert 18 AND alert 20 not active or refractory	Clears with valid sensor	"A sensor reading has not been received in the last 20 minutes. Please ensure that the phone is within range of the sensor."	20	-	After 1st re- fire	After 2nd re- fire	-
1 8	replace_transmitter: iPancreas sends message to replace the transmitter immediately 60 minutes after activation criteria for alert 17 if clear criteria has not been met	User acknowledgement	"The transmitt er is no longer functiona I. Please replace it immediat ely."	-	120	-	-	-
1 9	sensor_glucose_invalid: Sensor value is invalid for > 20 Minutes AND alert 19 AND alert 18 AND alert 20 not active or refractory	Clears with valid sensor	"Sensor value is not reporting correctly. Please	20	-	After 1st re- fire	After 2nd re- fire	-

			check your sensor site for problems . Contact the study coordinat or if needed."					
2 0	replace_sensor: iPancreas sends message to replace the sensor immediately 60 minutes after activation criteria for 19 if clear criteria has not been met	User acknowledgement	"The sensor may no longer be functioni ng. Please replace it immediat ely."	-	120	-	-	-
2	Insulin_pump_commun ication_failure: Basal Insulin Fails to deliver correct amount for 60 minutes OR insulin suspend required and no connection to pump	Successful basal insulin is delivered OR insulin is successfully suspended	"Insulin communi cation failure. Please move PDM and POD closer to phone"	60 min utes	If alert fires after 10:59 PM, refrac tory lasts until 6:59A M. No refrac tory other hours	After 1st re- fire	After 2nd re- fire	-

2	phone_battery_low:	If phone is	"Phone	10	of the day.	After	After	-
5	Phone battery falls below 20% AND is not charging	charging or level goes above 20%	battery low. Please charge"			1st re- fire	2nd re- fire	
6	maximum_insulin_exce eded: Insulin Delivery ≥ 35% TDIR _{adj} on last hour	Auto clears	"Max insulin has been exceeded "	-	60	Immedi ately	Immedi ately	-
7	cbg_equal_or_over_40 0: CBG ≥ 400 mg/dl AND alert 27 not active or refractory	Ketone check	"Blood glucose is above 400 mg/dl. Please change the insulin pod and check ketone levels now."	15	60	Immedi ately	Immedi ately	-
2 8	ketone_level_high: Ketones ≥ 0.6 mmol/L	User acknowledgement	"Ketone levels are high. If not already done, please change the insulin pod. Do	-	-	Immedi ately	Immedi ately	-

				not exercise.					
2 9	Insulin_pump_reservoir _low: Omnipod has less than 10% of fluid volume remaining.	Pod with greater than 10% volume is connected (i.e. pod is changed)		Your insulin pod is low. Please deactivat e your current pod and activate a new insulin pod.	120	-	After 1st re- fire	After 2nd re- fire	-
3 0	External_insulin_alert: iPancreas has determined that more insulin has been delivered than expected by observing the insulin pump' pulse count	None, this alert only goes to the study coordinato.	The app determined by the pump's pulse count that more insulin than was expected was delivered.	Alert for over-insulin delivery: The actual insulin exceeded the expected insulin by XX units.	-	-	Immedi ately	Immedi ately	-
3 1	Extreme_low_sensor_gl ucose: This alert fires when CGM is measured to be <= 54 mg/dL.	Measured CGM > 54 mg/dL.	This alert fires if CGM is measured to be < 54 mg/dL. When this alert is active, the sensor_glucose_lo w is suppressed.	"Sensor value is extremel y low" "Sensor glucose is below 54	10	30	After first re- fire	After second re-fire	-

Missed_meal_detection

_alert: This alert triggers

detects that carbohydrates

approximately 25 minutes

if the Missed Meal

were consumed

ago.

Detection algorithm

The user

acknowledges the

alert and either

doses insulin or

declines that a

20 minutes have passed since the

presumes the

consumed 25

minutes prior to the trigger. The alert will expire after 20 minutes from triggering.

meal was

dose

for?"

insulin

missed meal.

alert trigger.

D	ate. January .	31, 2022				
If CGM goes from <= 54 to between 70-54 mg/dL, the sensor_glucose_lo w alert will fire again after the refractory period of 30 minutes expires on the recently cleared extreme_low_sen sor_glucose alert	mg/dL. Please perform a blood glucose check now."					
The missed meal detection alert will trigger if glucose is rising rapidly and the prior carbohydrate intake is indicated by the algorithm. The algorithm	"Your glucose appears to be rising. Did you consume a meal that you want to	-	-	-	-	-

References

